To date, well over 500 patients with hematologic malignancies or solid tumors have been exposed to danvatirsen, and several doses, schedules, and infusion times have been evaluated. Both monotherapy and combination therapy with other anticancer agents have been studied. Consistent with the preclinical data, a bi-phasic pharmacokinetic (PK) profile was noted with an initial fast distribution phase (half-life of 2 to 3 hours) followed by a slower elimination phase. With regard to adverse events (AEs), risks included thrombocytopenia, liver enzyme elevations, anemia, and neutropenia. Overall, danvatirsen demonstrated a tolerable safety profile, and toxicities were well managed with standard guidelines.

The most relevant study of danvatirsen with regard to HNSCC is the SCORES study, which evaluated the addition of danvatirsen to checkpoint blockade. This study included both first-line and second-line patients with R/M HNSCC. The ORR was assessed in 66 evaluable patients treated with danvatirsen at a dose of 3 mg/kg weekly in combination with durvalumab in the first-line setting. In this patient population that was not selected for PD-L1 expression, ORR was 23% (CR 9.1%). The duration of response (DOR) was 42 weeks, indicating a clinically meaningful benefit. Considering that danvatirsen monotherapy in this anti-PD-L1 naïve HNSCC patient population showed no responses, and the historical ORR with durvalumab as monotherapy is also generally regarded as negligible, the combination of danvatirsen and durvalumab appeared to be active and well tolerated. Moreover, additional analyses showed an intriguing relationship between PD-L1 levels and ORR and CRs. In patients with CPS ≥ 1 or CPS ≥ 20 , the combination of danvatirsen and durvalumab led to an ORR of 31% to 37%, and 33% to 43%, respectively (note that the range is due to lack of CPS measures in some patients) and to a CR rate of 11% to 13% in the CPS ≥ 1 subgroup and 19% to 22% in the CPS ≥ 20 subgroup. These outcomes are numerically superior to pembrolizumab historical data in this population.

For the most up-to-date clinical information regarding danvatirsen, refer to the latest version of the Investigator's Brochure.

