5.5.1 Hematopoietic Growth Factors

Primary prophylactic use of granulocyte colony-stimulating factors is not permitted during Cycle 1 of treatment, but they may be used to treat treatment-emergent neutropenia as indicated by the current ASCO guidelines.

In subsequent cycles, the use of hematopoietic growth factors is at the discretion of the treating physician in line with local guidelines. Patients who enter the study on stable doses of erythropoietin or darbepoietin may continue this treatment, and patients may start either drug during the study at the discretion of the treating physician.

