9.6 Analysis of Safety

The analysis of safety will focus on AEs with summaries of TEAEs (i.e., AEs that start or increase in severity after the first dose of study treatment). AEs will be coded according to the latest Medical Dictionary for Regulatory Activities (MedDRA) version available at the time of database creation. The severity of AEs will be graded according to NCI CTCAE v5.0.

The number and percent of patients with any AE will be tabulated by system organ class and preferred term using MedDRA. AEs related to danvatirsen, AEs related to pembrolizumab, all SAEs, related SAEs, and AEs by maximum CTCAE grade will be summarized similarly.

Laboratory test results after the first dose of study treatment will be summarized by shift in CTCAE grade for laboratory parameters that can be graded. Laboratory parameters that cannot be graded by CTCAE will be summarized by shifts to low, normal, or high postbaseline.

Vital signs will be summarized by the change from baseline at each postbaseline timepoint. Descriptive statistics will be provided by study visit for physical examination, ECOG performance status, ECG, and weight parameters.

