### 5.13.2 Laboratory Data

All laboratory data will be stored in the database with the units in which they are originally reported. Laboratory data in summary tables and subject data listings will be presented in the International System of Units (SI units; Système International d'Unités).

Laboratory parameters will be programmatically graded according to NCI-CTCAE v5.0 toxicity grading, when applicable. For parameters for which a CTCAE scale does not exist, reference ranges from the local laboratory will be used to determine programmatically if a laboratory parameter is below, within or above the normal range for the subject's age and sex. In this case, values low, normal, or high will be assigned.

All laboratory result summaries will be presented separately for chemistry, hematology, coagulation, and urinalysis.

Change from Baseline of numerical laboratory results will be summarized at each visit. A separate summary for categorical urinalysis parameters will be provided.

Shift tables will be provided, showing change in CTCAE toxicity grade from Baseline to last visit as well as Baseline to worst post-Baseline grade. For parameters for which a CTCAE scale does not exist, the shift tables will instead present low, normal, or high, based on provided reference ranges of normal. Only patients with both a Baseline and post-Baseline assessment will be included in the analysis. Scheduled visits, unscheduled visits, and repeat assessments will be considered for worst post-Baseline grade.

In the event that a subject has post-Baseline lab results for the same parameter both above and below the range of normal, the record with the value that is the furthest from the reference range will be considered as the worst. If they are equidistant from the reference range, the worst post-Baseline will be assigned as high.

All hematology, chemistry, coagulation, and urinalysis data will be listed separately. An additional listing will be provided for abnormal laboratory values.

QMD Ref: Worldwide-TMP-ST-054-1.0_Effective: 12Aug2022	Governing QMD: Worldwide-SOP-ST-026
Confidentiality Statement	
This document is the property of Worldwide Clinical Trials Inc. and may not be duplicated, copied, altered or removed from company without prior approval from Worldwide Quality Assurance or in compliance with Worldwide Standard Operating Procedures.	

Worldwide Clinical Trials Controlled Quality Management Document			

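### As worded, the SAP rule for the worst laboratory result lets a high platelet or neutrophil count displace a severe low one in the baseline-to-worst shift table

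*SAP*

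**What the plan says.** SAP section 5.13.2 sets up two kinds of laboratory shift table. Parameters with a CTCAE scale get tables "showing change in CTCAE toxicity grade from Baseline to last visit as well as Baseline to worst post-Baseline grade". For parameters without one, "the shift tables will instead present low, normal, or high, based on provided reference ranges of normal".

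A separate paragraph then deals with patients who have abnormal results in both directions. It opens "In the event that a subject has post-Baseline lab results for the same parameter both above and below the range of normal" and rules that "the record with the value that is the furthest from the reference range will be considered as the worst". On ties: "If they are equidistant from the reference range, the worst post-Baseline will be assigned as high". The paragraph does not say which of the two kinds of parameter it covers, or how distance is measured.

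Protocol section 9.6 has no distance rule. It says that laboratory results "will be summarized by shift in CTCAE grade for laboratory parameters that can be graded". Protocol section 1.1.2 reports that with danvatirsen "risks included thrombocytopenia, liver enzyme elevations, anemia, and neutropenia".

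**The concern.** Distance from a reference range is not a measure of toxicity, and the two directions are not on an equal footing. A count can fall below the range by no more than the lower limit, because it cannot go below zero, whereas nothing caps how far it can rise above the range. A rule that keeps only the more distant record can therefore discard a severe low count in favour of a modestly raised one. The selected record lies above the range, so it carries no low-count grade.

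A high count in a patient who also had a low one is foreseeable. Of granulocyte colony-stimulating factors, protocol section 5.5.1 says that "they may be used to treat treatment-emergent neutropenia as indicated by the current ASCO guidelines", and Appendix 4 lists thrombopoietin receptor agonists among later treatments for immune thrombocytopenia. Patients treated for a low count are thus plausible candidates for a later high one.

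Clinical laboratory values are part of a secondary safety endpoint (protocol section 2). The haematology shift table, 14.3.5.2, is marked for the interim as well as the final output (SAP section 11). What is at stake is whether that table understates low counts in a subset of patients.

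**Working it through.** **Inputs.** The plan gives no figure to reproduce, and neither document gives reference ranges. I assume platelets with lower limit 130 to 150 and upper limit 400 to 450, and neutrophils with lower limit 1.5 to 2.0 and upper limit 7.0 to 8.0, all ×10^9/L. Low-platelet bands come from the immune thrombocytopenia rows of protocol Appendix 4 (Grade 3 from 25 to below 50, Grade 4 below 25), read in the same unit.

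**Formula.** Let L and U be the lower and upper limits, x the patient's lowest post-baseline value and y the highest. In measurement units the distances are L − x and y − U. With ties going to high, the high record is selected when

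y − U ≥ L − x, that is, y ≥ U + L − x.

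Since x cannot be below 0, any y ≥ U + L is selected whatever the low value was. The order of the two results plays no part.

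**Thresholds.**

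| Parameter and assumed range | High value that displaces the low value shown | High value that displaces every low value |
|---|---|---|
| Platelets 130–400, low 24 | 400 + 130 − 24 = 506 | 530 |
| Platelets 150–400, low 24 | 400 + 150 − 24 = 526 | 550 |
| Platelets 150–450, low 24 | 450 + 150 − 24 = 576 | 600 |
| Neutrophils 1.5–7.0, low 0.4 | 7.0 + 1.5 − 0.4 = 8.1 | 8.5 |
| Neutrophils 2.0–7.5, low 0.4 | 7.5 + 2.0 − 0.4 = 9.1 | 9.5 |
| Neutrophils 2.0–8.0, low 0.4 | 8.0 + 2.0 − 0.4 = 9.6 | 10.0 |

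**Example patients.**

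| Values | Assumed range | Distance below | Distance above | Record kept |
|---|---|---|---|---|
| Platelets 45 and 510 | 150–400 | 105 | 110 | High |
| Platelets 45 and 510 | 150–450 | 105 | 60 | Low |
| Platelets 20 and 590 | 150–450 | 130 | 140 | High |
| Platelets 20 and 500 | 150–450 | 130 | 50 | Low |
| Neutrophils 0.4 and 9.2 | 2.0–7.5 | 1.6 | 1.7 | High |
| Neutrophils 0.4 and 9.2 | 2.0–8.0 | 1.6 | 1.2 | Low |
| Neutrophils 0.4 and 9.5 | 1.8–7.5 | 1.4 | 2.0 | High |
| Neutrophils 0.4 and 8.5 | 1.8–7.5 | 1.4 | 1.0 | Low |

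Displacement is possible but not automatic, and it depends on the local range.

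**Does the metric matter?** Yes. On a fold scale the low record wins two of the cases kept as high above: platelets 150/20 = 7.5 against 590/450 = 1.31, and neutrophils 1.8/0.4 = 4.5 against 9.5/7.5 = 1.27. Dividing by the width of the range changes nothing, because both distances share the divisor: 130/300 = 0.433 against 140/300 = 0.467, and 1.4/5.7 = 0.246 against 2.0/5.7 = 0.351.

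**After the change proposed below.** The patient with platelets of 20 and 590 stays in the Grade 4 band, because the high value no longer competes with the low one.

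**Size per patient.** The planned combination arm is 54 (protocol Table 9), so each displaced patient is 1/54 = 1.9% of that arm. The documents give no figure for how many patients will have results on both sides of normal.

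**The case against.** The strongest reply is that the rule was never meant for graded parameters. The tie outcome, high, is a category of the low/normal/high scale and not a CTCAE grade. SAP section 5.2.11 speaks of a worst or maximum grade, and protocol section 9.6 calls for shifts in grade wherever a grade exists. On that reading platelets and neutrophils are untouched. This has real weight, and a reader who takes it as settled that the rule governs graded counts goes beyond the text. But section 5.2.11 deals with which visits count, not with how direction is chosen, and the paragraph in 5.13.2 carries no limit. Two programmers could reasonably implement it differently.

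A reader might also infer that the SAP prescribes raw distance. It does not: it names no metric, and on a fold scale the low value wins the cases tested. That omission is itself a gap.

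Finally, a reader might infer that severe low counts would disappear from the safety report. The documents do not support that. The baseline-to-last shift, the haematology and abnormal-value listings and the platelet and neutrophil spider plots are outside the rule. So are the adverse event tables, which take in low counts that meet the criteria of protocol section 7.9.5. These outputs do not fully replace the affected table, however. By-visit summaries leave out unscheduled and repeat tests (SAP 5.2.11), the baseline-to-last shift misses a low count that has recovered, and protocol section 7.9.5 keeps abnormalities that need no medical intervention out of the adverse event record.

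**Conclusion.** The point holds as a defect of wording with a possible effect on one descriptive table. Taken literally and with distance in units, the rule conflicts with the worst-grade shift promised in the same SAP section and with protocol section 9.6. It lets any platelet count of about 530 to 600 or more, or any neutrophil count of about 8.5 to 10.0 or more (×10^9/L), displace every low value. Those thresholds rest on assumed reference ranges. Only patients with results on both sides of normal are exposed, and only in the baseline-to-worst shift.

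If the rule is meant for ungraded parameters alone, the named danvatirsen risks are not affected. A patient who was both low and high on such a parameter would still be shown in one direction only. Neither reading supports a claim that the safety report as a whole understates thrombocytopenia or neutropenia, and no efficacy test or stopping rule depends on this table.

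**What to change.** In SAP section 5.13.2:

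- State that parameters with a CTCAE scale use the maximum post-baseline grade over all scheduled, unscheduled and repeat results, derived separately for the low and the high direction where both exist.
- For parameters without a CTCAE scale, report worst-low and worst-high as separate shifts.
- Remove the furthest-from-range rule and the rule that ties go to high.

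The cost is SAP wording, a matching change to the table shells and a few extra rows in the shift tables. No new data are needed. SAP section 5 provides for approved amendments before database lock; after lock the change would go into the post-lock addendum that the section describes.

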### 5.13.3 Vital Signs

Descriptive statistics for observed values and changes from Baseline in the following vital signs will be presented by study treatment arm and timepoint:

- Systolic blood pressure (mmHg)
- Diastolic blood pressure (mmHg)
- Pulse rate (bpm)
- Respiratory Rate (breaths/min)
- Temperature (degrees Celsius)
- Oxygen Saturation (%)
- Weight (kg)

All vital signs data will be listed.

### 5.13.4 Electrocardiogram Data

Descriptive statistics for observed values and changes from Baseline in the following ECG variables will be tabulated at each follow-up. Average of the triplicate will be used for the summaries.

- Heart rate (bpm)
- PR interval (ms)
- QRS duration (ms)
- QT interval (ms)
- QTc interval (ms)
- QTcF interval (ms)
- QTcB interval (ms)
- RR interval (ms)

Shift tables will be provided, showing the shift from Baseline to each scheduled visit in overall interpretation of the ECG. Overall Interpretation includes normal, abnormal and not clinically significant, and abnormal and clinically significant. Only patients with both a Baseline and post-Baseline assessment will be included in the analysis. Scheduled visits, unscheduled visits, and repeat assessments will be considered for worst post-Baseline grade.

QMD Ref: Worldwide-TMP-ST-054-1.0_Effective: 12Aug2022	Governing QMD: Worldwide-SOP-ST-026
Confidentiality Statement	

This document is the property of Worldwide Clinical Trials Inc. and may not be duplicated, copied, altered or removed from company without prior approval from Worldwide Quality Assurance or in compliance with Worldwide Standard Operating Procedures.

Worldwide Clinical Trials Controlled Quality Management Document			
 WORLDWIDE CLINICAL TRIALS	Sponsor:	Flamingo Therapeutics	
	Protocol Number:	FLM-6774-201	
STATISTICAL ANALYSIS PLAN			

A summary of ECG abnormalities will be provided for both the patient's last visit. The following categories for QTc/QTcF value (msec) will be summarized.

- $> 450$  and  $\leq 480$
- $> 480$  and  $\leq 500$
- $> 500$
- $> 30$  and  $\leq 60$  Increase from Baseline
- $> 60$  Increase from Baseline

All ECG data, including details of any abnormalities, will be listed.

### 5.13.5 Other Safety Assessments

The following data will be listed but not summarized.

- Physical Examination
- Endocrine Hormones
- Thyroid Function Test
- Non-Pharmacological Procedures
- Pregnancy Test
- Social History (Tobacco)
- Tumor Tissue Collection

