7.8.2 Clinical Laboratory Parameters

The hematology panel will consist of complete blood count (hemoglobin, hematocrit, erythrocytes [i.e., red blood cell count], and leukocytes [i.e., white blood cell count]) with differential (i.e., basophils, eosinophils, lymphocytes, monocytes, neutrophils) and platelet counts.

The clinical laboratory tests are listed in [Table 4](#); the timing and frequency of the laboratory tests are provided in the SoA ([Section 8.1](#)). These assessments should be performed at the local laboratory associated with the Investigator site.

Table 4: Clinical Laboratory Tests

Hematology	Chemistry	Coagulation	Urinalysis	Pregnancy Test	Other
Hemoglobin	ALT	INR			
Hematocrit	AST	aPTT or PTT			
WBC (with differential)	Alkaline phosphatase				
Neutrophils	Sodium				
Lymphocytes	Potassium				
Monocytes	Magnesium				
Eosinophils	Chloride				
Basophils	Total calcium				
RBC count	BUN or Urea				
Platelets	Creatinine				
	Glucose (non-fasted)				HIV viral load**
	Total bilirubin				
	Albumin				
	Phosphorous **(or phosphate)				
	LDH				
	Amylase**				
	Lipase**				
	Bicarbonate (or carbon dioxide)				
	Uric acid**				

* Morning, cortisol required at screening and when clinically indicated (adrenal insufficiency suspected). Blood sample should be drawn with ACTH.

** To be obtained only as clinically indicated for eligibility and throughout the study.

Abbreviations: ACTH = adrenocorticotrophic hormone; ALT = alanine aminotransferase; aPTT = activated partial thromboplastin time; AST = aspartate aminotransferase; BUN = blood urea nitrogen; HBV = hepatitis B virus; HCV = hepatitis C virus; HIV = human immunodeficiency virus; INR = international normalized ratio; LDH = lactate dehydrogenase; RBC=red blood cell; TSH = thyroid-stimulating hormone; WBC = white blood cell

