7.9.5 Clinical Laboratory Adverse Events

A clinical laboratory AE is any laboratory value that is deemed clinically significant by the Investigator and is accompanied by one of the following:

- Requires a medical intervention
- Requires a modification or interruption of study treatment
- Is accompanied by clinical symptoms

Laboratory abnormalities that do not require medical intervention should not be recorded as AEs and will be captured and reported in the laboratory section of the clinical study report (CSR). If a medical intervention occurs, it should be recorded as a treatment with the abnormal laboratory finding as the AE (e.g., anemia with treatment required and blood transfusion recorded as a procedure, hyperglycemia with treatment required and change in insulin dose recorded on the concomitant medications eCRF).

The Investigator should decide, based upon the AE criteria and the clinical condition of the patient, whether a change in a laboratory parameter is clinically significant and therefore represents an AE.

If, at the end of the treatment phase with the study treatment, there are pathological laboratory values that were not present at baseline, further clinical or laboratory investigations should be performed until the values return to within reference range or until a plausible explanation (i.e., concomitant disease) is found for the pathologic laboratory values.

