9.5 Disposition, Demographic and Baseline Characteristics, and Exposure

The number of patients in each study population and the reasons for exclusion will be summarized.

Patient demographics, baseline characteristics, and exposure will be listed and summarized for the FAS. Patient attributes will be summarized using frequency distributions for categorical variables or descriptive statistics for continuous endpoints, as appropriate.

Descriptive information for danvatirsen and pembrolizumab will be provided regarding the number of doses administered, the number of dose modifications and delays, the duration of treatment, and the relative dose intensity (% of treatment administered compared to targeted).

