## 5.11 Exposure and Compliance to Study Drug

Danvatirsen is an investigational medicinal product (IMP). Pembrolizumab is the standard of care. Collectively, these 2 drugs are referred to as the “study drug”.

The following exposure to study drug parameters will be summarized for the Safety Analysis Set for both Danvatirsen and Pembrolizumab

- Treatment Cycles Completed
- Treatment Duration (Months)
- Treatment Duration of Any Study Drug (Months)
- Number of Doses
- Number of Cycles Infusion Interrupted
- Number of Doses Delayed
- Number of Doses Skipped
- Dose Reductions (Danvatirsen only)

All study drug exposure data will be listed.

QMD Ref: Worldwide-TMP-ST-054-1.0_Effective: 12Aug2022	Governing QMD: Worldwide-SOP-ST-026
Confidentiality Statement	

This document is the property of Worldwide Clinical Trials Inc. and may not be duplicated, copied, altered or removed from company without prior approval from Worldwide Quality Assurance or in compliance with Worldwide Standard Operating Procedures.

Worldwide Clinical Trials Controlled Quality Management Document			
 WORLDWIDE CLINICAL TRIALS	Sponsor:	Flamingo Therapeutics	
	Protocol Number:	FLM-6774-201	
STATISTICAL ANALYSIS PLAN			

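### The SAP lists thyroid tests and physical examination without summarising them, and its exposure list omits relative dose intensity; the protocol calls for all three summaries and SAP 9 declares no change.

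*SAP*

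**What the plan says.** **Laboratory results.** Protocol 9.6 gives one rule for gradable tests, "Laboratory test results after the first dose of study treatment will be summarized by shift in CTCAE grade", and one for the rest: "Laboratory parameters that cannot be graded by CTCAE will be summarized by shifts to low, normal, or high postbaseline". Neither names or exempts a panel. SAP 5.13.2 restricts laboratory summaries to chemistry, hematology, coagulation and urinalysis. SAP 5.13.5 places thyroid function tests and endocrine hormones under the statement "The following data will be listed but not summarized".

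**Physical examination.** Protocol 9.6 names it, with ECOG status, ECG and weight, for descriptive statistics at each visit. SAP 5.13.5 puts it in the same listing-only group.

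**Exposure.** Protocol 9.5 asks for descriptive information on both drugs that includes "the relative dose intensity (% of treatment administered compared to targeted". SAP 5.2.10 gives the formula and the expected-dose rules. SAP 5.11 then introduces its list with "The following exposure to study drug parameters will be summarized for the Safety Analysis Set for both Danvatirsen and Pembrolizumab" and names eight items; relative dose intensity is not one of them.

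**Declared changes.** SAP 9 reports only that the final analysis is brought forward because the study was terminated early.

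**The concern.** Safety and tolerability of the combination is a secondary objective. Its endpoint in Protocol 2, repeated in SAP 2.1, names physical examinations and clinical laboratory values. Adding danvatirsen to a checkpoint inhibitor raises the question of whether immune toxicity changes, and Protocol Appendix 4 sets out thyroid toxicity grade by grade. A listing shows each patient's values but gives no count by arm.

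The adverse event tables do not fully close the gap. Protocol 7.9.5 says that laboratory abnormalities needing no medical intervention should not be recorded as adverse events; instead they "will be captured and reported in the laboratory section of the clinical study report". If the laboratory section tabulates only four other panels, mild thyroid changes are counted nowhere.

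Relative dose intensity matters for a different reason: it sets dose received against dose planned in one figure. For pembrolizumab, given in both arms, it would show whether adding danvatirsen reduces delivery of the standard treatment.

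**Working it through.** No sample size, power or error rate is involved, so the check is a comparison of text.

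1. **Are thyroid tests within the protocol's laboratory rule?** Protocol 9.6 does not name them, so this is an inference from three places. The notes to Table 4 (Clinical Laboratory Tests) include "TSH = thyroid-stimulating hormone". The Schedule of Activities marks thyroid function at screening, Day 1 of every cycle, end of treatment and the 30-day follow-up. Footnote f groups thyroid tests with the other predose assessments. Repeated post-baseline values therefore exist in both arms, and the general rule covers them.

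2. **Does any SAP table summarise them?** SAP 5.13.2 does not cover the panel and SAP 5.13.5 excludes it. SAP 11 gives Listing 16.2.8.6 for thyroid tests and Listing 16.2.8.5 for endocrine hormones, with no table title for either.

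3. **Which thyroid findings still reach a by-arm table?** Protocol 7.9.5 makes a clinically significant laboratory value an adverse event if it needs intervention, changes or interrupts study treatment, or comes with symptoms. SAP 5.13.1 tabulates treatment-emergent events by arm, including by maximum grade, Grade 3 or higher, and leading to dose delay or discontinuation. SAP 5.10 tabulates concomitant medication by actual treatment, so hormone replacement would show there too.

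4. **Which do not?** Appendix 4 supplies the example: Grade 1 primary hypothyroidism is TSH above 4.5 and below 10 mIU/L without symptoms, with pembrolizumab continued under monitoring. Such a patient meets none of the three triggers and appears in a listing only. The 7.9.5 sentence about intervention is narrower than the three triggers and the two fit together awkwardly, but this patient falls outside both.

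5. **Endocrine hormones.** Taking this group to be cortisol and ACTH, the Table 4 note reads: "Morning, cortisol required at screening and when clinically indicated (adrenal insufficiency suspected". Post-baseline values will exist only for patients in whom adrenal insufficiency was suspected.

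6. **Physical examination.** Of the four assessments Protocol 9.6 names for by-visit statistics, weight is summarised in SAP 5.13.3, ECG in SAP 5.13.4 and ECOG status in Table 14.3.7.5. Physical examination alone has only a listing (16.2.9.4).

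7. **Exposure.** Protocol 9.5 asks for number of doses, modifications and delays, duration, and relative dose intensity. SAP 5.11 covers the first three through cycles, two durations, doses, interruptions, delays, skips and reductions. The fourth, defined in SAP 5.2.10 as actual over expected cumulative dose × 100, is missing. No title in SAP 11 names it; Tables 14.3.6.1 and 14.3.6.2 are titled only as extent of exposure.

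**The case against.** The strongest reply is that little of clinical weight is lost, and most of it stands. A reader might infer that thyroid dysfunction would have no between-arm result. The documents do not support that: steps 3 and 4 show that only asymptomatic, untreated shifts go uncounted.

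It can also be said that Protocol 7.9.5 asks for such abnormalities to be reported, not tabulated, so Listing 16.2.8.6 satisfies it. That is fair for 7.9.5, but Protocol 9.6 separately says summarised by shift, and a listing does not do that.

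For endocrine hormones the reply succeeds. A shift table built on a few patients tested because of suspicion would not inform a comparison of arms.

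On relative dose intensity, a reader might infer that the analysis has been dropped. The SAP provides formulas for both drugs in a section describing derivations needed for analysis, which points to an oversight in 5.11. The table shells were not available and may carry it. Nor would every relative dose intensity result be comparative, since danvatirsen is given in one arm only. The tolerability component of the endpoint is dose interruptions and reductions, which SAP 5.11 does summarise.

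Finally, silence in SAP 9 breaches no protocol rule, because Protocol 9 places the description and justification of changes in the clinical study report. SAP 9 is nevertheless headed as the record of changes to the planned protocol analysis, and its reader would assume that these analyses follow the protocol.

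**Conclusion.** The point holds as a minor, correctable mismatch between protocol and SAP, in three parts:

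- **Thyroid tests** lack the shift summary that Protocol 9.6 requires. The loss is the by-arm count of asymptomatic, untreated biochemical change.
- **Physical examination** lacks the by-visit summary that Protocol 9.6 requires by name.
- **Relative dose intensity** is required by Protocol 9.5 and derived in SAP 5.2.10, but the SAP text does not commit to reporting it.

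The size cannot be put as a number of patients. It is tempting to cite the planned 81 (54 and 27 by arm), but those are planned maxima in a study that SAP 9 says was terminated early, and only patients with untreated, symptomless shifts are affected. The primary endpoint and its decision rule are untouched.

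The conclusion assumes that the general laboratory wording of Protocol 9.6 includes thyroid tests, that endocrine hormones means cortisol and ACTH, and that the unseen table shells do not already supply the missing summaries.

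**What to change.** 1. Move thyroid function tests from SAP 5.13.5 to 5.13.2 and add a baseline-to-worst low/normal/high shift table by arm. Count low and high separately. The current 5.13.2 rule keeps only the value furthest from the reference range, so a patient who goes from thyrotoxicosis to hypothyroidism, a course that Appendix 4 describes, would be counted in one direction only.
2. Keep endocrine hormones as a listing. Declare this in SAP 9, giving as the reason that post-baseline samples are taken only when clinically indicated.
3. Add descriptive statistics for relative dose intensity, for each drug, to SAP 5.11 and to Tables 14.3.6.1 and 14.3.6.2. Compare arms for pembrolizumab only. No percentage cut-off is needed; neither document sets one.
4. Either summarise physical examination by visit, as Protocol 9.6 states, or declare the change in SAP 9.

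The cost is one extra shift table and a few rows in existing tables, plus a physical examination summary if that option is chosen. The data are already collected for the listings. Under SAP 5 the amendment needs approval before database lock; after that it belongs in the post-lock addendum.
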